2.2.4 Statistical hypothesis, model, and method of analysis

CV death

The statistical hypothesis is:

$H_0: \lambda_2/\lambda_1 \geq 1$, i.e., the rate of primary event of CV death is greater or equal in the serelaxin group relative to the placebo group *versus the one-sided alternative* $H_A: \lambda_2/\lambda_1 < 1$, i.e., the rate of CV death is smaller in the serelaxin group relative to the placebo group, where λ_1 and λ_2 are the hazard rates for CV death in the placebo group and serelaxin group, respectively. The ratio λ_2/λ_1 is also called the hazard ratio of serelaxin to placebo.

The hypothesis will be tested based on the FAS with a log rank test at an initial significance level of $(4/5)\alpha$ within a sequentially rejective multiple testing procedure described in detail in [Section 2.2.6.4](#). Note that the significance level for the final test will be adjusted to account for the planned interim analysis.

Number and percentage of subjects who died from cardiovascular reasons based on the number of subjects in the population as denominator will be provided by treatment group. The hazard ratio (relative risk) and its associated two-sided 95% confidence interval will be estimated based on a Cox proportional hazards model with treatment assignment as a factor.

The Kaplan-Meier estimates of the survival functions for each treatment group will be plotted. The Kaplan-Meier estimates of the cumulative event rate will also be presented in tables by treatment group for each day and also by time interval.

WHF

Time to worsening heart failure (WHF) through Day 5 will be analyzed using Gehan's generalized Wilcoxon test at an initial significance level of $(1/5)\alpha$ within a sequentially rejective multiple testing procedure described in detail in [Section 2.2.6.4](#).

Number and percentage of patients who experienced WHF based on the number of patients in the population as denominator will be provided by treatment group. The hazard ratio (relative risk) and its associated two-sided 95% confidence interval will be estimated based on a Cox proportional hazards model with treatment as a factor.

Kaplan-Meier curves will be presented graphically by treatment group and Kaplan-Meier estimates for selected time points with 95% confidence intervals will be tabulated.

Model assumption

For *primary efficacy* variables analyzed by Cox proportional hazard model, the important model assumption that is made when applying a Cox proportional hazards regression model is the proportionality of the hazard function(s) over time. This assumption will be tested using the same primary Cox proportional hazards regression model and in addition a time-dependent explanatory variable created through the interaction between log time and treatment. In addition, a graphical method will be used for checking the proportional hazards assumption. A plot of log-log survivor function vs. log time for each treatment group will be used. Approximate parallelism between the curves for the treatment groups will provide supportive evidence of the proportional hazards assumption. It should be noted that the log rank test remains valid even if the proportional hazards assumption is not fulfilled.

The SAS procedures PHREG and LIFETEST will be used to conduct the analyses.

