### 10.4.2 Statistical model, hypothesis, and method of analysis

#### CV death

Time-to-event is computed as the number of days from randomization to CV death. Patients without an event will be censored at the earlier of the last date at which the vital status was known or Day 180. Patients who die from a non-cardiovascular cause before Day 180 will be censored at the time of death.

The statistical hypothesis is:

$H_0: \lambda_2/\lambda_1 \geq 1$ , i.e., the rate of primary event of CV death is greater or equal in the serelaxin group relative to the placebo group *versus the one-sided alternative*  $H_A: \lambda_2/\lambda_1 < 1$ , i.e., the rate of CV death is smaller in the serelaxin group relative to the placebo group, where  $\lambda_1$  and  $\lambda_2$  are the hazard rates for CV death in the placebo group and serelaxin group, respectively. The ratio  $\lambda_2/\lambda_1$  is also called the hazard ratio of serelaxin to placebo.

The hypothesis will be tested based on the FAS with a logrank test at an initial significance level of  $(4/5)\alpha$  within a sequentially rejective multiple testing procedure described in detail in Section 10.5.1. Note that the significance level for the final test will be adjusted to account for the planned interim analysis.

Number and percentage of patients who died from cardiovascular reasons based on the number of patients in the population as denominator will be provided by treatment group. The hazard ratio (relative risk) and its associated two-sided 95% confidence interval will be estimated based on a Cox proportional hazards model with treatment assignment as a factor.

The Kaplan-Meier estimates of the survival functions for each treatment group will be plotted. The Kaplan-Meier estimates of the cumulative event rate will also be presented in tables by treatment group for each day and also by time interval.

The SAS procedures PHREG and LIFETEST will be used to conduct the analyses [*SAS/STAT User's Guide, version 9.3*].

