Amendment 3	03-Mar-2017	
 - Add a new protocol deviation “ Site closed down for GCP reasons” leading to exclusion from the FAS and PPS -Subjects without valid written informed consent will be excluded from all analysis populations. - Remove covariate lymphocytes (%) from covariate-adjusted sensitivity analysis of CV death because of a number of missing values at baseline

List of abbreviations

ACE	Angiotensin Converting Enzyme
ACM	All-cause mortality
AE	Adverse Event
AHF	Acute Heart Failure
ALP	Alanine Phosphatase
ALT	Alanine Aminotransferase
ARB	Angiotensin-II Receptor Blocker
AST	Aspartate Aminotransferase
ATC	Anatomical Therapeutic Chemical
BNP	Brain Natriuretic Peptide
BPDE	Blood pressure decrease event
BUN	Blood Urea Nitrogen
CBPDE	Confirmed blood pressure decrease event
CCU	Coronary care unit
CEC	Clinical Endpoints Committee
CI	Confidence interval
CPK	Creatine Phosphokinase
CRF	Case Report Form
CSR	Clinical Study Report
█	█
CV	Cardiovascular
CVD	CV death
CVDR	CV death or rehospitalization due to heart failure or renal failure
CWHF	Clinical Worsening Heart Failure
dL	Deciliter
DMC	Data Monitoring Committee
DRE	Disease-related event
ECG	Electrocardiogram
EF	Ejection fraction
eGFR	Estimated Glomerular Filtration Rate
FAS	Full Analysis Set
GCP	Good Clinical Practice
HF	Heart failure
ICU	Intensive Care Unit
ITT	Intent-to-treat
IV	Intravenous
kg	Kilogram
LFT	Liver Function Toxicity
LOS	Length of hospital stay
LPLV	Last Patient Last Visit

LSM	Least-square Mean
MAP	Master Analysis Plan
MedDRA	Medical Dictionary for Regulatory Activities
MRA	Mineralocorticoid receptor antagonist
mg	Milligram
min	Minute
mL	Milliliter
mmHg	Millimeters mercury
NYHA	New York Heart Association
OF	O'Brien-Fleming
PASS	Physicians Assessment of Signs and Symptoms
PD	Protocol Deviation
PPS	Per Protocol Set
PT	Preferred Term
RAN	Randomized Set
RAP	Report and Analysis Preparation
RBC	Red Blood Cell
SAE	Serious adverse event
SAF	Safety Set
SAS	Statistical Analysis System
SBP	Systolic Blood Pressure
SCR	Screened Set
SGOT	Glutamic Oxaloacetic Transaminase
SGPT	Glutamic Pyruvic Transaminase
sMDRD	Simplified Modification of Diet in Renal Disease
SMQ	Standardized MedDRA Query
SOC	System Organ Class
TBL	Total Bilirubin
ULN	Upper Limit of Normal
WHF	Worsening heart failure
WHO-DD	World Health Organization Drug Dictionary
µg	Microgram

1 Introduction

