2.2.5 Supportive/sensitivity analyses for primary endpoint

- Both primary efficacy variables, CV death and WHF through Day 5, will also be analyzed on the PPS as supportive information.
- To explore the consistency of treatment effects across subgroups, the CV death and WHF will also be analysed for respective subgroups provided in Table 2.3 by adding the subgroup and the treatment by subgroup interaction terms to the Cox regression model of the primary efficacy endpoint. In all analyses a test for heterogeneity to assess for possible interactions between treatment and baseline variables will be applied. Results will be presented graphically as forest plots. The objective of the subgroup analyses is to evaluate the consistency of treatment effects across a wide variety of patient groups.
- A covariate-adjusted Cox-regression model will be fitted for the CV death with baseline covariates (Age (continuous), history of heart failure (yes/no), cerebrovascular accident (yes/no), respiratory rate (continuous), systolic BP (continuous), edema (categorical), orthopnea (categorical), sodium (continuous), creatinine (continuous)) identified from

RELAX-AHF exploratory analysis ([Metra, et al 2013](#)) to account for other factors that might affect prognosis using likelihood ratio test for treatment effect with exact handling of ties.

- Analyses will be performed using a modified definition of WHF, e.g. subjects with (1) worsening signs AND symptoms or (2) IV intervention and/or mechanical support. Another sensitivity analyses that exclude subjects whose only symptom is abdominal bloating/discomfort or fatigue/decreased exercise tolerance will also be provided.
- Subjects with WHF through Day 5 (yes/no) will also be analyzed using logistic regression with treatment and region as factors.

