2.2.6 Key secondary analysis

There are three key secondary efficacy variables defined in this study.

All key secondary variables will be analyzed using the FAS and PPS populations, and will be repeated for the subgroups provided in Table 2-3 by adding the subgroup and the treatment by subgroup interaction terms to the model for time to event endpoints.

Whenever the event or visit time needed for defining the time-to-event or censoring date and time is missing or incomplete, an imputation rule for missing/incomplete time will be applied. More details about the imputation rule are presented in [Section 2.2.9](#).

2.2.6.1 Time to all-cause death through Day 180

Time to all-cause death will be calculated as:

Time-to-event (days) = date of all-cause death – randomization date,

The analysis will be performed similarly to primary endpoint.

For those subjects without events, the censoring date will be the earliest in the following dates:

- **180 days**
- **Date subject withdrew consent to all follow-up (if no subsequent vital status documented)**

Note: in accordance with local laws and regulations, vital status may be publically available

- **Date of subject's last visit or contact or vital status**

A covariate-adjusted Cox-regression model similar to the sensitivity analysis of primary efficacy variable will also be performed as sensitivity analysis.

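### CV death is tested with an unadjusted log-rank test although nine baseline covariates are already prespecified for it; using them in the primary test would be a cheap, modest gain in power

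*SAP*

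**What the plan says.** SAP 2.2.4 and Protocol 10.4.2 use the same primary test for CV death. The SAP wording is "The hypothesis will be tested based on the FAS with a log rank test", and the Protocol wording is "The hypothesis will be tested based on the FAS with a logrank test". The reported hazard ratio is "estimated based on a Cox proportional hazards model with treatment assignment as a factor", so it too is unadjusted.

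SAP 2.2.5 then adds, as a supportive analysis: "A covariate-adjusted Cox-regression model will be fitted for the CV death with baseline covariates". The list has nine items: age, history of heart failure, cerebrovascular accident, respiratory rate, systolic BP, edema, orthopnea, sodium and creatinine. They were taken from an exploratory analysis of the preceding trial. SAP 2.2.6.1 repeats the model for all-cause death: "A covariate-adjusted Cox-regression model similar to the sensitivity analysis of primary efficacy variable will also be performed as sensitivity analysis".

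The SAP's change history for Amendment 3 records one covariate taken out: "Remove covariate lymphocytes (%) from covariate-adjusted sensitivity analysis of CV death because of a number of missing values at baseline". Under SAP 2.1.3 a missing baseline value is replaced by the screening value. Neither document says what happens to a covariate that is missing at both times.

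WHF is handled differently. Time to WHF "will be analyzed using Gehan's generalized Wilcoxon test at an initial significance level of" one fifth of alpha, and the only adjusted analysis is this: "Subjects with WHF through Day 5 (yes/no) will also be analyzed using logistic regression with treatment and region as factors".

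**The concern.** Prognostic differences between patients that the test ignores are treated as noise. When strong baseline predictors have been measured and fixed in advance, a test that uses them gives a larger expected Z from the same patients and events.

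The ingredients are already there. Medical and heart failure history (Protocol 6.2), vital signs (6.5.2), edema and orthopnea (6.4.4.1) and local sodium and creatinine (6.5.4.2) are collected in all patients, not in a substudy. The covariates and their forms are prespecified.

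CV death drives the sample size, and its power at its own initial level of one-sided 0.02 is only about 80%. Protocol 10.7 and SAP 2.5 foresee that the event rate may be lower than planned and would respond by changing the number of patients randomized. Adjustment offers a smaller protection without enrolling anyone.

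**Working it through.** **Inputs from the documents.** 6,800 patients, 1:1; 180-day placebo CV death rate 9.0%; hazard ratio 0.78; one interim at 329 CV deaths (60%); Z boundaries 2.786 and 2.072; one-sided 0.02.

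**Step 1: reproduce the plan.**
- Expected CV deaths: 3,400 × [0.09 + (1 − 0.91^0.78)] = 3,400 × (0.0900 + 0.0709) = 547. This agrees with 329/0.6 = 548. The planned total itself is blacked out.
- Event proportion: 547/6,800 = 8.05%.
- Lan-DeMets O'Brien-Fleming boundaries at one-sided 0.02 and 60% information: 2.786 and 2.072, as stated.
- Boundary hazard ratios: exp(−2 × 2.786/√329) = 0.7355 (stated 0.735); exp(−2 × 2.072/√548) = 0.838 (as stated).
- Expected Z: 0.2485 × √547 / 2 = 2.906. Power at 0.02 is 80.3% for a fixed design and 80.1% group-sequentially. With alpha passed on from the other endpoints it is 81 to 82%, against 82% in most rows of SAP Table 2-11 B. That last figure needs assumed weights for part of the testing graph, because the figure is not shown.

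The plan's power claim is therefore sound for the test it names.

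**Step 2: approximate the gain.** A covariate-adjusted log-rank test subtracts from each patient's log-rank score its regression on the covariates. For a normal prognostic score with log-hazard standard deviation σ and event proportion p, the information gain is roughly σ²p, with σ ≈ √2 × Φ⁻¹(C). The C-index is an assumption.

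| C | σ² | gain = σ² × 0.0805 |
|---|---|---|
| 0.60 | 0.128 | 1.0% |
| 0.65 | 0.297 | 2.4% |
| 0.72 | 0.679 | 5.5% |
| 0.77 | 1.092 | 8.8% |

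**Step 3: simulate the test itself.** Two separate runs used 6,800 patients, nine normal covariates, a 9.0% placebo rate, a marginal hazard ratio of 0.78 and rejection at Z > 2.072, ignoring the interim. Each scenario had 2,500 trials. The top scenario had C about 0.75 to 0.77 in the first run and 0.77 in the second. The gain is the squared ratio of mean Z.

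| C | mean Z, run 1 | gain | power, run 1 | mean Z, run 2 | gain | power, run 2 |
|---|---|---|---|---|---|---|
| 0.65 | 2.934 → 2.971 | 2.5% | 80.1 → 81.8% | 2.885 → 2.921 | 2.5% | 78.9 → 79.9% |
| 0.72 | 2.873 → 2.945 | 5.1% | 79.2 → 81.2% | 2.869 → 2.954 | 6.0% | 79.4 → 81.8% |
| about 0.77 | 2.868 → 2.989 | 8.6% | 79.3 → 82.6% | 2.896 → 3.021 | 8.8% | 79.7 → 83.7% |

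Under the null the adjusted test rejected in 1.6% of 2,500 trials and 1.95% of 4,000, against a nominal 1.91%. No inflation was seen.

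**Step 4: put the gain on the design.** Power is Φ(2.906 × √gain factor − 2.072), starting from 79.8% unadjusted.
- Factor 1.01: 80.2% (+0.4 points).
- Factor 1.025: 80.8% (+1.0).
- Factor 1.06: 82.1% (+2.3).
- Factor 1.09: 83.2% (+3.4).

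The raw simulated differences run from +1.0 to +4.0. The +1.7 at C 0.65 in run 1 is partly simulation noise, since that run's mean Z values imply +1.0. In events: 548 × 0.025 = 14 and 548 × 0.09 = 49.

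**Step 5: effect on the published boundary hazard ratios.** With 2.5 to 9% more information, Z = 2.072 corresponds to exp(−2 × 2.072/√(548 × 1.025)) = 0.840 up to exp(−2 × 2.072/√(548 × 1.09)) = 0.844, instead of 0.838.

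**The case against.** The strongest reply is that nothing is broken. The log-rank test is valid, the power was computed for it, and the stated power is reached. Which valid test is primary is a design choice, and adjusted evidence is already planned as support. All of this stands, and it is why the point is an improvement and not a defect.

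The size is also open to challenge. No C-index appears in the documents. Eligibility limits systolic BP and eGFR (Protocol 4.1 and 4.2), which narrows the range of two of the nine covariates. Lymphocytes have been removed, and several of the nine are binary or categorical, whereas the simulation used normal ones. The upper end of the range may therefore not be reached.

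A change of test also touches more than one sentence. The interim analysis and the boundary hazard ratios belong to the unadjusted statistic, and an adjusted p-value beside an unadjusted confidence interval could disagree. These objections stand and are met in the fix.

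One common objection does not apply. An adjusted Cox test would change the hazard ratio to a conditional one, whereas the adjusted log-rank test keeps the unadjusted null and the marginal effect.

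A reader might infer that both primary endpoints are affected. The documents do not support that. SAP 2.2.5 specifies the nine covariates for CV death only, nothing shows that they predict 5-day WHF, and a covariate-adjusted Gehan test has not been evaluated here.

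**Conclusion.** The point holds for CV death alone, as a cheap improvement. The primary test leaves out covariates that the SAP has already fixed for the same endpoint. Using them adds about 2.5 to 9% information, or about 1 to 4 power points on roughly 80%, if their joint C-index is 0.65 to 0.77. At 0.60 the gain is about 0.4 points. The direction of the gain is not in doubt; its size rests on that assumed C-index, on normal covariates in the simulation and on ignoring the interim.

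Two stronger readings should be resisted. The trial is not shown to be underpowered, because its stated figures reproduce. Nor would patients be saved in a trial already sized at 6,800: the equivalent of 14 to 49 CV deaths describes precision gained, not a smaller sample.

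**What to change.** Set the following before unblinding, in SAP 2.2.4, 2.2.5, 2.4 and 2.5 and Protocol 10.4.2, 10.6 and 10.7.

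1. Make the covariate-adjusted log-rank test, with the nine covariates of SAP 2.2.5 in their listed forms, the primary test of CV death. Keep the unadjusted log-rank test as a sensitivity analysis.
2. Where a covariate is still missing after the screening value has been used, fill it with the pooled median or mode, blind to arm. Without this rule a complete-case analysis would drop patients and events.
3. Use the same statistic at the interim and final analyses, with the Z boundaries 2.786 and 2.072 unchanged, and mark the hazard ratios 0.735 and 0.838 as approximate. The documents do not say whether the interim had taken place by SAP Amendment 3 (03-Mar-2017). If it was done with the unadjusted test, either justify the mixed sequence or keep the unadjusted test.
4. Report the marginal hazard ratio with a confidence interval that matches the adjusted test, beside the unadjusted Cox hazard ratio.
5. Leave the WHF test as it is.

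The cost is wording in both documents, a short program and renewed agreement with regulators on the primary test. If the covariates predict weakly, the return is under 1 point. If the sponsor prefers to keep the unadjusted test, a sentence recording why is enough.

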2.2.5 Supportive/sensitivity analyses for primary endpoint

- Both primary efficacy variables, CV death and WHF through Day 5, will also be analyzed on the PPS as supportive information.
- To explore the consistency of treatment effects across subgroups, the CV death and WHF will also be analysed for respective subgroups provided in Table 2.3 by adding the subgroup and the treatment by subgroup interaction terms to the Cox regression model of the primary efficacy endpoint. In all analyses a test for heterogeneity to assess for possible interactions between treatment and baseline variables will be applied. Results will be presented graphically as forest plots. The objective of the subgroup analyses is to evaluate the consistency of treatment effects across a wide variety of patient groups.
- A covariate-adjusted Cox-regression model will be fitted for the CV death with baseline covariates (Age (continuous), history of heart failure (yes/no), cerebrovascular accident (yes/no), respiratory rate (continuous), systolic BP (continuous), edema (categorical), orthopnea (categorical), sodium (continuous), creatinine (continuous)) identified from

RELAX-AHF exploratory analysis ([Metra, et al 2013](#)) to account for other factors that might affect prognosis using likelihood ratio test for treatment effect with exact handling of ties.

- Analyses will be performed using a modified definition of WHF, e.g. subjects with (1) worsening signs AND symptoms or (2) IV intervention and/or mechanical support. Another sensitivity analyses that exclude subjects whose only symptom is abdominal bloating/discomfort or fatigue/decreased exercise tolerance will also be provided.
- Subjects with WHF through Day 5 (yes/no) will also be analyzed using logistic regression with treatment and region as factors.

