### 10.4.4 Supportive analyses

In addition to the primary analyses, the primary efficacy variable, CV death and WHF will also be analyzed using the same primary analysis model on the Per Protocol set as supportive information. Subgroup (age [65 and 75 cut off], gender, race, region, PEF/REF, naïve vs prior history of HF) analyses will be analyzed for both primary endpoints for FAS.

The survival function for each treatment arm will be estimated by the Kaplan-Meier-technique and the Kaplan-Meier curves will be presented for both FAS and PP. The proportion of patients with a primary endpoint will be estimated from the Kaplan-Meier curve for each treatment.

Sensitivity analyses will also be performed using a modified definition of WHF, for example where both signs and symptoms are present.

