2.2 Efficacy evaluation

The primary analysis and the analyses of all secondary efficacy endpoints will be based on the FAS population following the intention-to-treat principle.

[figure not shown]

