- Time-to-event (days) = date of CV death – randomization date,

For those subjects without events, the censoring date will be the earliest in the following dates:

- **180 days**
- **Date subject withdrew consent to all follow-up (if no subsequent vital status documented)**

Note: in accordance with local laws and regulations, vital status may be publically available

- **Date of non-CV death**
- **Date of subject's last visit or contact or vital status**

The censoring time for the analyses will be calculated as:

- Time-to-event censored (days) = censoring date – randomization date

Whenever the event date or visit date needed for defining the time-to-event or censoring date is missing or incomplete for a given subject, an imputation rule for missing/incomplete date will be applied. More details about the imputation rule are presented in [Section 2.2.9](#).

2.2.3 Time to worsening heart failure (WHF) through Day 5 (considering death in the 5-day period as WHF event)

WHF events occurring within 120 hours of randomization will be included in the analysis. WHF is defined as clinical worsening of HF during the index hospitalization or as adjudicated rehospitalization for HF. A subject who dies by 120 hours without a WHF event will be considered to have had an event at the time of death.

Event date and time will be used at calculating the time to event for better precision, and convert it back to days.

Time-to-event (days) = (first event date/time – randomization date/time),

For those subjects without events the censoring date will be the earliest in the following dates:

- **Hour 120 (5 days)**
- **Date subject withdrew consent to all follow-up**
- **Date of subject's last visit or contact**

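### One WHF sensitivity analysis, as worded, drops randomized subjects because of the symptoms of a post-randomization WHF episode, when it should stop counting the episode and keep the subject

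*SAP*

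**What the plan says.** SAP 2.2.5 describes two kinds of WHF sensitivity analysis in one bullet. The first changes the event: "Analyses will be performed using a modified definition of WHF, e.g. subjects with (1) worsening signs AND symptoms", with IV intervention and/or mechanical support as the other example. The second follows as a separate analysis: the SAP says that sensitivity analyses that "exclude subjects whose only symptom is abdominal bloating/discomfort or fatigue/decreased exercise tolerance will also be provided".

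Nothing in SAP 2.2.5 or elsewhere says whether the episode is recoded as a non-event, whether the subject stays at risk afterwards, or whether a later qualifying episode or death counts.

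The surrounding rules are these:

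- SAP 2.2: "The primary analysis and the analyses of all secondary efficacy endpoints will be based on the FAS population following the intention-to-treat principle".
- SAP 2.2.3: "WHF events occurring within 120 hours of randomization will be included in the analysis", and "A subject who dies by 120 hours without a WHF event will be considered to have had an event at the time of death".
- SAP 2.1.1 allows exclusions from the full analysis set (FAS) beyond misrandomized subjects only in exceptional circumstances. Tables 2-1 and 2-2, which list the reasons for removal from analysis sets, contain no symptom criterion.
- Protocol 10.4.4: "Sensitivity analyses will also be performed using a modified definition of WHF, for example where both signs and symptoms are present". It does not mention leaving subjects out.

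**The concern.** Every eligible patient has persistent dyspnea at screening and at randomization (Protocol 4.1, criterion 3), so having bloating or fatigue as the only symptom cannot sensibly describe baseline. The condition must refer to the WHF episode. Only patients who have already had an event can meet it, and treatment may influence which of them do.

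Deleting those patients has two effects that recoding the episode does not have. It takes randomized patients out of the denominator and the risk set because of their outcome. It also discards what happens to them afterwards. Once a soft-symptom episode no longer counts as WHF, a death by 120 hours in the same patient would be an event under SAP 2.2.3; if the patient is deleted, that death is lost.

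The question behind the analysis is a fair one. WHF is a primary endpoint, and the in-hospital part rests on clinical worsening judged at the bedside; the event committee's remit in Protocol 9.5 covers deaths and rehospitalizations. An analysis of whether the result depends on soft symptoms should keep the randomized comparison intact.

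**Working it through.** **Inputs from the documents.** 6,800 patients randomized 1:1, so 3,400 per arm (SAP 2.5, Protocol 5.2). Placebo WHF rate 12.2% and assumed hazard ratios (HRs) of 0.70 and 0.80 (SAP Table 2-10). One-sided WHF alpha 0.005 initially (SAP 2.2.6.4) and 0.6 × 0.025 = 0.015 once CV death is rejected (SAP Table 2-9).

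**Reproducing the plan's own figure.** The serelaxin rate is 1 − (1 − 0.122)^HR. At HR 0.80 this is 9.89%, which gives 3,400 × (0.122 + 0.0989) ≈ 751 events. The logrank approximation is power = Φ(√(events/4) × |ln HR| − z). At HR 0.80 it gives 68.5% at alpha 0.005 and 81.3% at 0.015; SAP Table 2-11 states 81 to 82%. At HR 0.70 there are 711 events and the power is 98.5% and 99.5%; the table states 99%. The design inputs are therefore read correctly. No stated figure is in dispute.

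**Assumptions.** The documents do not give the following, so they are varied:

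- f: share of WHF patients whose only symptoms are the named ones, 5% to 30%.
- q: share of those patients with a later qualifying WHF or death by 120 hours, 0 or 30%.

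**Formulas, per arm with WHF rate p.**

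- Patients removed: 3,400 × p × f.
- Episode not counted: events = 3,400 × p × (1 − f) + q × removed; denominator 3,400.
- Subject excluded: events = 3,400 × p × (1 − f); denominator 3,400 − removed.
- HR = ln(1 − serelaxin rate) / ln(1 − placebo rate).

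**Worked case, f = 10% in both arms, q = 0.** Removed: 41.5 placebo and 33.6 serelaxin. Episode not counted: 10.98% against 8.90%, HR 0.801. Subject excluded: 11.12% against 8.99%, HR 0.799.

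| f placebo / serelaxin | q | Removed placebo / serelaxin | HR, episode not counted | HR, subject excluded | Shift |
|---|---|---|---|---|---|
| 5% / 5% | 0 | 21 / 17 | 0.8006 | 0.7995 | −0.001 |
| 10% / 10% | 0 | 41 / 34 | 0.8011 | 0.7990 | −0.002 |
| 20% / 20% | 0 | 83 / 67 | 0.8022 | 0.7980 | −0.004 |
| 30% / 30% | 0 | 124 / 101 | 0.8033 | 0.7970 | −0.006 |
| 30% / 30% | 30% | 124 / 101 | 0.8023 | 0.7970 | −0.005 |
| 20% / 5% | 0 | 83 / 17 | 0.9603 | 0.9405 | −0.020 |
| 20% / 5% | 30% | 83 / 17 | 0.9045 | 0.9405 | +0.036 |
| 5% / 20% | 0 | 21 / 67 | 0.6688 | 0.6784 | +0.010 |
| 5% / 20% | 30% | 21 / 67 | 0.7093 | 0.6784 | −0.031 |

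With equal shares, about 38 to 225 randomized patients are dropped and the HR hardly moves. With unequal shares the shift is larger, and its sign depends on q, so exclusion cannot be called conservative in advance.

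**The case against.** The strongest reply is that nobody meant to delete patients. In the preceding sentence, subjects with certain features stands for subjects counted as WHF events, so excluding subjects could mean not counting them as events. The protocol plans only modified definitions, the efficacy analyses use the FAS, SAP 2.2.4 takes the whole population as the denominator for WHF percentages, and the exclusion tables have no symptom criterion. This reading is plausible. It does not settle the text, because the SAP uses exclusion for removal from analysis populations in 2.1.1, 2.1.2, 2.3.2.1 and 2.3.4, and a programmer could follow either reading.

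A second reply also stands in part. A subject who later has an episode with dyspnea no longer has bloating or fatigue as the only symptom and arguably would not be excluded. On that reading, the lost events shrink to deaths by 120 hours and later episodes with no other symptom. The q = 30% rows therefore illustrate the reading in which the first episode decides. The documents support no count of hard events lost.

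A reader might also infer that the analysis could give no reassurance at all about soft symptoms. The figures do not support that. When shares are equal the two versions nearly agree. In the 20% / 5% case both show most of the assumed benefit gone (0.94 excluded; 0.96 or 0.90 not counted, from a design value of 0.80), so dependence on soft symptoms would still be visible.

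**Conclusion.** The defect is real but limited. As worded, the analysis selects on a post-randomization outcome and departs both from the SAP's FAS and intention-to-treat basis and from the protocol's modified-definition approach. Neither document contains a recoding rule that would rescue it.

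The size rests on assumed shares. The HR shift is about 0.001 to 0.006 for equal shares of 5% to 30%. It is about 0.02 to 0.04 for 20% on placebo against 5% on serelaxin, and about 0.01 to 0.03 for the reverse, in either direction.

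Two wider conclusions are not supported. The primary WHF test and the type I error are unaffected, because this analysis is supportive and lies outside the multiple testing procedure. The other modified-definition analyses in the same bullet are not shown to share the fault, because they change what counts as an event and do not say that anyone is removed.

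**What to change.** Replace the second sentence of the bullet in SAP 2.2.5 with wording such as: *Episodes whose only symptoms are abdominal bloating/discomfort or fatigue/decreased exercise tolerance are not counted as WHF; the subject stays in the FAS and remains at risk for the first qualifying WHF or death through 120 hours.*

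If recoding was the intention all along, this only writes it down. It costs one SAP sentence, needs no new data, and should be settled before unblinding. The other modified definitions need no change on this account.
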